During the COVID-19 pandemic, and in keeping with the overall primary objective, the study will be a single-arm, non-randomised trial piloting a remotely delivered version of the active intervention of early hearing aid provision and support to test recruitment, feasibility and acceptability .

5 Trial design

The trial is a randomised controlled pilot trial. 76 participants with mild cognitive impairment and hearing loss will be randomised on a 1:1 ratio to the TACT Hearing Intervention of home-based hearing assessment, timely hearing aid fitting, and psychological and practical support to sustain adherence to treatment, versus a Healthy Ageing Intervention (HAI), whereby the participant will be given information about their hearing impairment and advised to consult with their GP to obtain NHS audiological treatment, as well as being provided with one-to-one sessions with a researcher (matching the intensity of social contact of the Hearing Intervention) on behavioural changes that can promote healthy ageing and may reduce risk of progression from MCI to dementia.

Participants for the pilot trial will be aged 55 years or above and recruited from memory clinics with a diagnosis of mild cognitive impairment, who have evidence of hearing loss as per audiologist

[figure not shown]
assessment, and who are willing to be treated with hearing aids if appropriate following audiology assessment. Assessments will take place in people's homes. Figure 3 presents the expected flow of participants through the trial.

The duration of follow-up in this pilot trial will be 6 months. People who abandon hearing aid use do so shortly after starting treatment, typically during the first few weeks of being fitted with aids. Conversely, there is evidence that behavioural health change, when sustained for 6 months or more is likely to be permanent [15], and therefore that adherence to hearing aids at trial end is likely to provide a valid estimate of longer term compliance. It is expected that participants allocated to the Hearing Intervention will be able to sustain adherence to hearing aids. The trial objective of 70% adherence to hearing aids treatment in the hearing intervention at 6 months, if met, will be a strong indicator that adherence is solidly established and that a longer duration definitive trial is feasible. We envisage the duration of a fully-powered trial to be 2 to 3 years.

Non-blinding of assessors

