8.2 Randomisation Procedures

Following participant consent, and confirmation of eligibility at the screening visit (see section 8.1 for pre-treatment assessments), the participant will be allocated a participant trial number and the randomisation procedure described below will be carried out. An independent statistician will generate the randomisation list which will be uploaded to REDCap (an online randomisation database) for online concealed allocation. Participant randomisation will then be undertaken centrally by the coordinating team using REDCap. Participants will be randomised to either the Hearing Intervention or Healthy Ageing Intervention by computer programme on a 1:1 ratio. The randomisation list and the Trial Subject Log will be kept by the trial manager. The audiologist will receive by secure communication the participant's allocation to the Hearing or Healthy Ageing Intervention.

Participants are considered to be enrolled into the trial following: consent, pre-treatment assessments (see section 8.1), confirmation of eligibility, completion of the randomisation process, allocation of

the participant trial number and intervention by the central coordinating team.

The RHI sub-study (during COVID-19) will not be randomised. All participants will be allocated to the RHI.

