11.3 Sample size calculation

This pilot trial will assess the feasibility of proceeding to the future definitive RCT of sufficient duration to detect differences in cognitive changes between arms. The main feasibility questions that the pilot aims to answer are: (a) is the trial feasible, in the sense of resulting in sufficiently high recruitment, randomisation and sufficiently low dropout at 6 months; (b) is the Hearing Intervention deliverable and acceptable to participants; (c) estimate the difference in hearing aid use at 6 months between the Hearing Intervention and Healthy Ageing Intervention arms to inform sample size estimates for the future trial. We are including cognitive outcomes to assess their feasibility and acceptability, and to provide estimates including standard deviation to be used in the sample size calculation for the full trial. As a feasibility study, the current trial is not powered to detect differences in the cognitive outcomes between the arms. Therefore, only descriptive analyses will be performed using the data collected. No formal power calculation is necessary, and instead the sample size has been determined as to provide sufficient precision (sufficiently narrow confidence intervals) for trial estimates of recruitment and randomisation, dropout, acceptability of the intervention, and difference in hearing aid usage between arms, as detailed below.

With 76 randomised participants, we will achieve the following 95% confidence intervals (CI) for our expected estimates of recruitment, randomisation, dropout, acceptability of the intervention, and difference in hearing aid adherence between the Hearing Intervention and Healthy Ageing Intervention at the end of trial [88]:

1. Recruitment and randomisation of eligible participants with a MCI diagnosis from NHS community memory clinics. Target: 50% of eligible participants will be randomised; with n=76 recruited subjects the 95% CI would be [39-61].
2. Follow-up: target of 80% randomised participants with complete follow-up at 6 months,

95%CI with n=76 would be [71-89].

3. Acceptability of the Hearing Intervention: proportion of participants allocated to the Hearing Intervention completing ≥ 2 intervention sessions – expected value $\geq 80\%$ of intervention group, 95% CI with n=76 would be [71-89].

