4. Difference in daily hearing aid adherence between arms: target of 50% difference between the Hearing Intervention and Healthy Ageing Intervention arms in the proportions of participants maintaining hearing aid use at 6 months (end of follow-up), 95% CI with n=76 would be [31-69].

Mean, proportions, differences in means and proportions with corresponding 95% confidence intervals will be calculated as appropriate for the cognitive scales and other trial outcomes, to inform the sample size calculation for a full scale trial.

Criteria for the decision of progression to the main trial

We judge that these confidence intervals provide acceptable ranges to inform continuation to the main trial. The final decision to “go” or “stop”, that is, whether to proceed or not to the main trial, will be taken by the Trial Steering Committee after the end of trial and with consideration of whether the trial has met its primary and secondary outcomes, as well as any lessons learnt during the pilot.

As a **guidance to this decision**, we anticipate that if the 4 endpoint estimates above in this section, as measured in the pilot trial, fall within their respective expected confidence intervals as detailed above, this will be a “go” signal for a full scale trial. If the endpoint estimates fall up to 10% below the lower limit of their target confidence interval (as detailed above in this section) we will consider whether modifications to the trial design to improve these endpoints would be sufficient to remediate these issues when proceeding to the main trail. If any of these endpoints fall below these minimal rates this will be a “do not progress to RCT” signal.

The Remote Hearing Intervention sub-study (COVID-19) will contribute to this decision by providing initial descriptive data and a qualitative assessment on the feasibility and acceptability of a remote version of the Hearing Intervention.

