11.4 Planned recruitment rate

To reach the target sample size of 76 randomised participants, and assuming recruitment rate of 50%, 152 potential participants will need to be approached during the 78 weeks of recruitment, or just under 2 potential participants per week.

The recruitment base will be five NHS London memory services, with 600 MCI patients per year (four times the screening target). Camden & Islington Memory Services alone exceed 1200 new patient referrals per year, of which 20% have MCI (or 240 people per year). We estimate that based on these five patient identification centres, the referral rate will be approximately six potential participants per week; two participants will be suitable and will agree to participate (one per research assistant). We conducted a small (n=12) feasibility study with similar but less restrictive inclusion and exclusion criteria as the proposed trial. This study recruited seven participants in four weeks, of which five had been confirmed to have untreated hearing loss and would have met inclusion criteria for the planned trial (1.25 potential participant per week), based on a single memory service, so the projected figures should be achievable.

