11.6.2 Primary outcome analysis

We will produce estimates and 95% Confidence Intervals for:

- Recruitment: Number of participants who will be randomised into the trial, divided by the total number of screened participants, expressed as percentage
- Retention: Number of participants that do not drop out before 6 month endpoint assessment, divided by the total number of randomised participants, expressed as percentage
- Acceptability of the Hearing Intervention: proportion of participants allocated to the Hearing Intervention completing ≥ 2 intervention sessions, divided by the total number of participants randomised to the Hearing Intervention.

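### Section 11.3 computes the acceptability and recruitment planning intervals on 76, but their denominators are 38 and 152, so two guidance progression limits are not the interval limits they are said to be

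*Protocol*

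**What the plan says.** Section 11.3 makes no power calculation. It rests the sample size on the precision of the planned estimates and says that with 76 randomised participants "we will achieve the following 95% confidence intervals (CI) for our expected estimates". Four intervals follow:

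- Recruitment, 50% of eligible participants randomised: "with n=76 recruited subjects the 95% CI would be [39-61".
- Retention at 6 months, 80% of randomised participants: 71 to 89.
- Acceptability, 80% of those allocated to the Hearing Intervention completing at least two sessions: "of intervention group, 95% CI with n=76 would be [71-89".
- Adherence difference between arms, 50 points: "95% CI with n=76 would be [31-69".

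Other sections fix the denominators. Section 5 says "76 participants with mild cognitive impairment and hearing loss will be randomised on a 1:1 ratio", and section 8.2 repeats the ratio. Section 11.6.2 analyses acceptability as a count "divided by the total number of participants randomised to the Hearing Intervention". Section 11.1 defines recruitment as randomised over eligible. Section 11.4 starts from 76 randomised and a 50% rate and concludes that "152 potential participants will need to be approached during the 78 weeks of recruitment".

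The closing part of 11.3 turns these intervals into guidance. An estimate inside its interval signals go, one up to 10% below the lower limit prompts consideration of modifications, and anything lower signals do not progress. The Trial Steering Committee takes the final decision.

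**The concern.** The figure 76 is the total randomised. It is the right denominator for retention, but acceptability is measured in one arm only, and for recruitment the 76 are the numerator. If both intervals were computed on 76 regardless, the stated precision is wrong for two of the three primary outcomes.

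This matters for two reasons. The intervals are the only justification offered for the sample size. Their lower limits also reappear as the guidance limits for progression, so a denominator error passes into a rule that the committee will be asked to apply.

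**Working it through.** **Inputs.** Total randomised 76, allocated 1:1 (sections 5 and 8.2), hence 76/2 = 38 per arm; the 38 is derived, not printed. Targets are 50% recruitment, 80% retention and 80% acceptability (11.1, 11.3). Expected adherence is 70% against 20% (11.2). At the 50% target the recruitment denominator is 76/0.50 = 152, the figure in 11.4. Confidence level 95%, z = 1.96.

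**Formula.** One proportion: p ± 1.96 × √(p(1−p)/n). Difference: (p1−p2) ± 1.96 × √(p1(1−p1)/n1 + p2(1−p2)/n2).

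**Step 1: reproduce the plan's figures.**

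- Recruitment, p = 0.5, n = 76: half-width 1.96 × √(0.25/76) = 11.2 points, giving 38.8 to 61.2. This matches 39 to 61.
- Retention, p = 0.8, n = 76: half-width 1.96 × √(0.16/76) = 9.0 points, giving 71.0 to 89.0. This matches, and 76 is the right denominator.
- Acceptability, p = 0.8, n = 76: the same 71.0 to 89.0. This matches, but only with 76 as denominator.
- Adherence difference, 38 per arm: half-width 1.96 × √(0.21/38 + 0.16/38) = 19.3 points, giving 30.7 to 69.3. This matches 31 to 69. With 76 per arm it would be 36.3 to 63.7, which does not match.

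So the section used the arm size for the adherence difference but the trial total for acceptability, although both carry the label n=76.

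**Step 2: use the protocol's own denominators.**

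- Acceptability, n = 38: half-width 1.96 × √(0.16/38) = 12.7 points, giving 67.3 to 92.7. The stated 9.0 points would need 76 people in the Hearing Intervention arm, that is 152 randomised.
- Recruitment, n = 152: half-width 1.96 × √(0.25/152) = 7.9 points, giving 42.1 to 57.9.

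**Step 3: does the interval method explain the gap?** No. For 80% at n = 38, Wilson gives 64.8 to 89.7, and Clopper-Pearson at 30/38 gives 62.7 to 90.5. For 50% at n = 152, Wilson gives 42.2 to 57.8 and Clopper-Pearson 41.8 to 58.2. None returns the stated interval.

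**Step 4: effect on the guidance limits, in counts at the planned size.**

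- Acceptability: the lower limit of 71% needs 27/38 (71.1%); 67.3% needs 26/38 (68.4%). So 26/38 is modify as written and go on the correct interval.
- Recruitment: the lower limit of 39% needs 60/152 (39.5%); 42.1% needs 64/152. So 60 to 63 of 152 is go as written and modify on the correct interval.
- Do-not-progress floors: if the 10% means percentage points, they move from 61 to 57 (acceptability) and from 29 to 32 (recruitment). If it is relative, they move from 63.9 to 60.6 and from 35.1 to 37.8.

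**The case against.** The strongest reply is that little depends on these figures. The limits are labelled guidance, and the Trial Steering Committee weighs all outcomes and the lessons learnt. Section 11.6.2 already divides acceptability by the Hearing Intervention arm, so the reported estimate and its interval will not inherit the error. For acceptability the printed limit differs from the corrected one by a single participant and is the stricter of the two. For recruitment the stated interval is wider than the true one, so the sample size gives more precision on that endpoint than claimed. The printed 71% and 39% could also stand as thresholds in their own right. All of this stands, and it lowers the weight of the point. It does not make the two intervals correct, and the rule presents these numbers as confidence limits, which they are not.

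A second reply is that 152 is loosely labelled: 11.4 calls these people approached, 11.1 and 11.3 say eligible, and 11.6.2 says screened. That is fair, and the terms need reconciling. But 76/0.50 = 152 holds for whichever group carries the 50% target, and under none of the three terms is the denominator 76.

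A reader might go further and infer that the adherence-difference interval is wrong too, because 80% follow-up would leave about 30 per arm and an interval of 28 to 72. The documents do not support that. The interval is introduced as what 76 randomised participants give, and 38 per arm reproduces it. The smaller denominator assumes that only participants with complete follow-up are analysed, which the protocol does not fix: self-report may stand in for missing data logging, an early discontinuation visit is attempted, and further detail is left to the statistical analysis plan.

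**Conclusion.** Two of the three primary-outcome planning intervals in 11.3 are wrong as written. Acceptability should be 67 to 93 and not 71 to 89, so its half-width is about 1.4 times the stated one (12.7/9.0). Recruitment should be 42 to 58 and not 39 to 61, so its half-width is about 0.7 times the stated one (7.9/11.2). Retention and the adherence difference are correct for 76 randomised.

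Because the errors run in opposite directions, the guidance scheme is neither uniformly strict nor uniformly lenient: its lower go limit is about 4 points too high for acceptability and about 3 points too low for recruitment, relative to the intervals it claims to use.

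This should be fixed, but it is not critical. It would be too strong to infer that the trial's analysis is compromised or that a binding stop rule is faulty, since the limits guide a committee decision and the acceptability analysis is correctly specified. The result assumes the planned 76 randomised in equal arms, the target rates as stated, and the Wald formula that reproduces the protocol's figures.

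**What to change.** In 11.3:

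1. Restate acceptability as 67 to 93 with n = 38 in the Hearing Intervention arm, and recruitment as 42 to 58 with n = 152 at a 50% rate. Leave retention and the adherence difference unchanged, noting that the latter uses 38 per arm.
2. Use one term for the recruitment denominator in 11.1, 11.3, 11.4 and 11.6.2, in place of eligible, screened and approached.
3. Write the progression limits as explicit percentages. Either keep 71% and 39% as pre-stated thresholds separate from the confidence intervals, or say openly that they move to 67% and 42%. Correcting the arithmetic should not shift a decision limit unnoticed.

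The cost is a change of numbers and wording; design, data collection and analysis are untouched. The one downside is that the stated precision for acceptability becomes less favourable, and moving its limit to 67% would relax that go signal.

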11.5 Randomisation methods

Individual-level randomisation with randomly varying block sizes to ensure equal number of participants allocated to each intervention arm.

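### Section 11.3 gives the acceptability interval for n=76, but the endpoint is measured in the Hearing arm only (about 38), so its planned precision is overstated

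*Protocol*

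**What the plan says.** Section 11.3 makes no power calculation. It justifies the sample size by the width of the confidence intervals for four named estimates, and acceptability of the Hearing Intervention is the third. Item 3 defines it as the proportion of those allocated to the Hearing Intervention who complete at least two sessions, expects at least 80%, and gives the precision as "of intervention group, 95% CI with n=76 would be [71-89"].

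Section 11.6.2 fixes the denominator for the same outcome: "divided by the total number of participants randomised to the Hearing Intervention". Section 5 says "76 participants with mild cognitive impairment and hearing loss will be randomised on a 1:1 ratio", and section 11.5 describes "randomly varying block sizes to ensure equal number of participants allocated to each intervention arm".

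The progression guidance at the end of section 11.3 reuses the four intervals. Estimates that "fall within their respective expected confidence intervals as detailed above" are a 'go' signal. Up to 10% below the lower limit means considering modifications to the design. Any endpoint below that gives a signal not to progress. The Trial Steering Committee takes the decision, and the rule is described as guidance to it.

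**The concern.** The population of the endpoint and the n behind its interval do not match. Acceptability can be observed only in the Hearing arm, yet its interval is the same as that of item 2 (retention), whose denominator really is all 76 randomised.

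Two things depend on the figure. First, it is part of the only justification offered for the sample size, and acceptability is one of the three primary outcomes in section 11.1. Second, its lower limit becomes a progression limit, so the 71% floor is presented as a 95% confidence limit for a quantity that will be estimated from half as many people.

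**Working it through.** **Inputs.** Total randomised 76 (sections 5 and 11.3); allocation 1:1 with blocking for equal arms (sections 5 and 11.5), so 38 in the Hearing arm; expected proportion 0.80 (section 11.3, item 3); expected adherence 70% and 20% (section 11.2 b), used for a cross-check.

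**Step 1: reproduce the printed interval.** Wald formula, p ± 1.96 × √(p(1−p)/n).
- n = 76: 1.96 × √(0.16/76) = 0.090, giving 71.0 to 89.0. This is the printed [71-89].

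**Step 2: same formula, Hearing-arm denominator.**
- n = 38: 1.96 × √(0.16/38) = 0.127, giving 67.3 to 92.7, or [67-93].
- The half-width is 12.7 points instead of 9.0, larger by √2 = 1.41.
- The choice of method does not explain the printed figure. At 80% of 38, Wilson gives 64.8 to 89.7, Clopper-Pearson 63.9 to 91.2 and continuity-corrected Wald 66.0 to 94.0.

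**Step 3: is n=76 just a label for the size of the trial?** Item 4 carries the same label.
- 38 per arm: 0.50 ± 1.96 × √(0.21/38 + 0.16/38) = 30.7 to 69.3, the printed [31-69].
- 76 per arm: 36.3 to 63.7, which does not match.

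Item 4 was computed with 38 per arm under an n=76 label. Item 3 was computed with 76. The label is therefore used in two ways in one list, and item 3 cannot be read as a 38-person calculation.

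**Step 4: effect on the progression limits with 38 people.**
- 'Go' floor: 71% needs 27/38 (71.1%); 67.3% needs 26/38 (68.4%).
- Lower edge of the modify band, reading 10% as percentage points: 61% needs 24/38 (63.2%); about 57% needs 22/38 (57.9%). On that reading 23/38 (60.5%) is a signal not to progress as printed, and in the modify band if the limits are re-derived.
- Reading 10% as relative: 0.9 × 71 = 63.9% and 0.9 × 67.3 = 60.6%.

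**Step 5: behaviour of the 'go' floor** (binomial, n = 38).

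| True rate | P(reach go), floor 71% | P(reach go), floor 67% |
|---|---|---|
| 80% | 93.8% | 97.1% |
| 75% | 77.7% | 86.8% |
| 70% | 52.4% | 65.9% |
| 65% | 27.4% | 39.9% |

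At a true 80% the chance of missing 'go' is 6.2% with the 71% floor and 2.9% with the 67% floor.

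**The case against.** The strongest reply is that little turns on this. The rule is guidance, the Trial Steering Committee also weighs the other outcomes and the lessons learnt, and a result just below 71% leads to considering modifications, not to stopping. The floor would move by one participant. The error is also conservative: 71% is stricter than 67%, so the printed lower limit cannot create an unwarranted 'go'. All of this stands, and it limits the severity. It does not make the printed interval right.

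Three stronger readings are tempting, and the documents do not support them.

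- *The slip is confined to item 3.* A reader might infer this because item 4 was computed correctly. But item 1 also uses n=76, for a proportion whose denominator is eligible participants (screened participants in section 11.6.2). Section 11.4 puts the number to be approached at 152 for a 50% rate. At 50% with n = 152 the Wald interval is 42.0 to 58.0, not [39-61]. That is a separate matter, but the rest of the list cannot be taken as sound.
- *The progression limits are invalid and should simply be lowered to 67 and 57.* A sponsor may choose 71% as a threshold; only its description as a 95% limit fails. The section 2 summary reports 36 participants randomised with complete data, and section 5 says assessors are not blinded. Lowering the floor now would loosen the rule after outcome data exist.
- *The trial needs more participants.* Section 11.3 names no required half-width, so ±12.7 points cannot be called inadequate on the protocol's own terms.

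**Conclusion.** The interval in section 11.3, item 3, is wrong for the endpoint it describes. With the Hearing arm as denominator it is [67-93], and the planned half-width is 12.7 points, not 9.0. As a result the 71% floor in the progression guidance is not the 95% limit of this endpoint. No estimate or analysis changes, and the effect on the decision rule is one participant at the 'go' floor. It should be fixed, but it does not threaten the trial.

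Assumptions: exactly 38 in the Hearing arm (random block sizes could shift this by one or two) and the Wald formula that the protocol evidently used. The 57% figure also needs 10% to mean percentage points. The correction describes the plan for 76. If randomisation in fact ended at the 36 reported in the summary (an assumption, since the protocol still states 76), the Hearing arm would be about 18 and the interval about 62 to 98, which is further from the printed figure.

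**What to change.** In section 11.3, item 3, give n=38 and [67-93] in place of n=76 and [71-89].

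In the progression guidance, keep 71% and the band 10% below it for acceptability, but declare them as chosen thresholds, not as limits derived from a confidence interval. If the sponsor prefers to re-derive the limits (about 67%, and about 57% if 10% means percentage points), the protocol should say that this loosens the rule after 36 participants already had complete open-label data.

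Check the n used in item 1 at the same time.

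Cost: a line or two of text and a less favourable statement of precision. No extra participants, data or analyses are needed.
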